4.3.3. Replacements

Patients who withdraw or discontinue will not be replaced.

5. STUDY TREATMENTS

5.1. PART A: PLACEBO-CONTROLLED TREATMENT PERIOD

5.1.1. Method of Assigning Participants to Treatment Groups

Patients will be randomly assigned at the baseline visit (Day 1) to receive losmapimod (active drug) or placebo using a 1:1 allocation ratio. Randomization will be stratified to ensure that treatment allocation is balanced across FSHD repeat number categories (ie, 1 to 3 repeats versus 4 to 9 repeats) and by FSHD Type (FSHD1 versus FSHD2).

An Interactive Response Technology (IRT) system will be used to administer the randomization schedule. A designated unblinded statistician separate from the study team will generate the randomization schedule using the latest version of SAS software (SAS Institute, Cary, NC) for IRT, which will link sequential patient randomization numbers to treatment codes. The randomization will use an appropriate block size, which will not be revealed.

Patients can be randomized only once.

5.1.2. Treatments Administered

Study drug tablets (losmapimod or placebo) will be dispensed to patients at the visits detailed in [Table 7](#).

During the 48-week placebo-controlled treatment period, patients will receive 15 mg losmapimod PO BID or placebo BID with food.

If a patient misses a dose and it is more than 6 hours until the next planned dose, the patient will be instructed to take the missed dose and resume study drug dosing as normal. If it is less than 6 hours until the next planned dose, the patient will be instructed to skip the missed dose and then resume study drug dosing as normal.

On visit days during which blood collection will occur for PK assessment (see [Table 7](#)), patients should wait to take their dose in the clinic.

5.2. PART B: OPEN-LABEL EXTENSION

5.2.1. Treatments Administered

Losmapimod will be dispensed to patients at the visits detailed in [Table 8](#). Patients are not to receive study drug until all assessments for Part A have been completed.

While on study, patients will receive 15 mg losmapimod tablets PO BID with food.

If a patient misses a dose and it is more than 6 hours until the next planned dose, the patient will be instructed to take the missed dose and resume study drug dosing as normal. If it is less than 6 hours until the next planned dose, the patient will be instructed to skip the missed dose and then resume study drug dosing as normal.

Any planned treatment interruptions (e.g., scheduled surgery) during Part B may be permitted on a case-by-case basis with approval from the Medical Monitor.

5.3. IDENTITY OF INVESTIGATIONAL PRODUCT

Losmapimod tablets for oral administration are available as [REDACTED]
[REDACTED] tablets containing 15 mg of losmapimod as the [REDACTED] free base. Losmapimod tablets also contain the inactive excipients [REDACTED]
[REDACTED]
[REDACTED]

Placebo tablets (Part A only) are identical in appearance to losmapimod and are manufactured using commonly used and recognized tablet excipients that are also used in the active tablets.

An IRT system will be used to ensure that the study site is provided with adequate supplies of blinded losmapimod and placebo (Part A only) or losmapimod (Part B only) and that no expired tablets will be dispensed to study patients.

5.4. MANAGEMENT OF CLINICAL SUPPLIES

5.4.1. Study Drug Packaging and Storage

All tablets are packed in white high-density polyethylene bottles with a child-resistant closure and include an induction sealed liner.

Each dispensation will contain a blinded (Part A only) or labeled (Part B only) dosage for 1 patient with a sufficient quantity to cover until the next scheduled visit plus additional tablets to cover the visit window. If needed, patients may be provided additional study drug via a courier service, as applicable. Study drug will be packaged and labeled in accordance with regulatory requirements. In Part A only, study drug will be packaged and labeled in a manner to retain the study blind.

Further details of study drug packaging, labeling, and distribution of the study medication will be provided in the Pharmacy Manual. For information on proper storage of the study drug, refer to the current losmapimod Investigator's Brochure or Pharmacy Manual.

5.4.2. Study Drug Accountability

During the study, each patient will be provided a sufficient quantity of study drug to allow for dosing until their next scheduled visit plus additional tablets to cover the visit window. If needed, patients may be provided additional study drug via a courier service, as applicable. At the next scheduled clinic visit, patients must return their bottles of study drug for accountability.

The Investigator will maintain accurate records of receipt of all study drug, including dates of receipt. In addition, accurate records will be kept regarding when and how much study drug is dispensed and used by each patient in the study. Reasons for departure from the expected dispensing regimen must also be recorded. At the completion of the study, to satisfy regulatory

requirements regarding drug accountability, all study drug will be reconciled and retained or destroyed according to applicable regulations.

5.5. LIFESTYLE RESTRICTIONS

Strenuous physical activity (eg, heavy lifting, weight or fitness training) should be avoided for 48 hours prior to each study visit. Routine ambulatory and other activities (eg, walking at normal pace) will be permitted, with the level of activities kept as similar as possible on all days of the study.

For the screening visit in Part A and the baseline visit in Part B, patients will be required to fast for at least 4 hours prior to laboratory blood samples being taken.

5.5.1. Contraception Requirements

A female patient of childbearing potential is eligible to participate if she is using or willing to use a highly effective method for avoidance of pregnancy for the duration of dosing and until [REDACTED] after the last dose of study drug.

Women of childbearing potential and male patients with female partners of childbearing potential must agree to use one of the contraception methods listed in [Section 5.5.1.1](#). This criterion must be followed from the time of the first dose of study medication until [REDACTED] after the last dose of study drug.

5.5.1.1. Highly Effective Methods for Avoiding Pregnancy in Females of Childbearing Potential

The following is the all-inclusive list of highly effective methods for avoiding pregnancy (ie, have a failure rate of less than 1% per year when used consistently and correctly and, when applicable, in accordance with the product label) ([Hatcher 2007](#)):

- Combined (estrogen and progestogen containing) hormonal contraception associated with inhibition of ovulation:
 - Oral
 - Intravaginal
 - Transdermal
- Progestogen-only hormonal contraception associated with inhibition of ovulation:
 - Oral
 - Injectable
 - Implantable
- Intrauterine device
- Intrauterine hormone-releasing system
- Bilateral tubal occlusion

- Vasectomized partner, provided that the partner is the sole sexual partner of the WOCBP trial patient and that the vasectomized partner has received medical assessment of the surgical success
- Sexual abstinence (Sexual abstinence is considered a highly effective method only if defined as refraining from heterosexual intercourse during the entire period of risk associated with the study treatments. The reliability of sexual abstinence needs to be evaluated in relation to the duration of the clinical trial and the preferred and usual lifestyle of the patient.)

Periodic abstinence (calendar, symptothermal, post-ovulation methods), withdrawal (coitus interruptus), spermicides only, and lactational amenorrhoea method (LAM) are not acceptable methods of contraception. Progestogen-only oral hormonal contraception (where inhibition of ovulation is not the primary mode of action), male or female condom with or without spermicide, and cap, diaphragm or sponge with spermicide are not considered as highly effective. A combination of male condom with either cap, diaphragm, or sponge with spermicide (double barrier methods) are not considered highly effective, birth control methods.

5.6. BLINDING

5.6.1. Part A: Placebo-Controlled Treatment Period

The placebo-controlled treatment period will be performed in a double-blind fashion. The Investigator, study staff, patients, and monitor will remain blinded to patient-level treatment assignment until study closure. The Sponsor and/or its designee will remain blinded to the treatment until after all patients have completed Part A of the study and the database has been locked for statistical analyses, after which time they will be unblinded.

The study drug and its matching placebo are indistinguishable and will be packaged in the same way. There are no tolerability issues that could unblind drug versus placebo.

A patient's treatment assignment will not be broken until the end of the study unless medical treatment of the patient depends on knowing the study treatment the patient received. In the event that the blind needs to be broken because of a medical emergency, the Investigator may unblind an individual patient's treatment allocation without the Sponsor's prior agreement. As soon as possible, the Investigator should contact the Medical Monitor to discuss the medical emergency and the reason for revealing the actual treatment received by that patient.

For medical emergencies, the treatment assignment will be unblinded through the IRT. Reasons for treatment unblinding must be clearly explained and justified in the eCRF. The date on which the code was broken together with the identity of the person responsible must also be documented.

Patients who continue to Part B will remain blinded to their Part A treatment condition through completion of Part B.

5.6.2. Part B: Open-Label Extension

Neither patients nor study staff will be unblinded to Part A treatment condition. Patients will not be blinded in Part B.

5.7. TREATMENT COMPLIANCE

Patient compliance will be monitored by tablet counts in the clinic. In addition, patient diaries may be used to record the date and time of each dose taken. This information may also be used to calculate compliance. Site staff should encourage the proper use of study drug for those patients who are not compliant.

5.8. PRIOR AND CONCOMITANT THERAPY

Use of all concomitant medications taken within 28 days before screening through the safety follow-up visits will be recorded in the patient's eCRF. The minimum requirement is that drug name and the dates of administration are to be recorded. This will include all prescription drugs, herbal products, vitamins, minerals, and over-the-counter medications. Any changes in concomitant medications also will be recorded in the patient's eCRF.

Any concomitant medication deemed necessary for the welfare of the patient during the study may be given at the discretion of the Investigator. However, it is the responsibility of the Investigator to ensure that details regarding the medication are recorded in full in the eCRF.

The use of the following medications is restricted or prohibited in this study:

- Vaccination with a live attenuated vaccine from 6 weeks prior to randomization until the safety follow-up visits.
- Patients who are on drug(s) or supplements that may affect muscle function, as determined by the Investigator, or that are included in the list of drugs presented in [Appendix 3](#) must be on a stable dose of that drug(s) or supplement for at least 3 months prior to the first dose of study drug and remain on that stable dose for the duration of the study. Changes to the dose or treatment discontinuation during the study can only be done for strict medical reasons by the treating physician with clear documentation and notification to the Sponsor. Treatment with a statin can be initiated during the study if it is medically required. In this case, preference should be given to hydrophilic statins (e.g., pravastatin, rosuvastatin, fluvastatin) over lipophilic statins (e.g., simvastatin, atorvastatin, lovastatin.) Particular attention should be paid to creatine phosphokinase (already part of the laboratory safety monitoring) in patients who start treatment with a statin during the study.

Subjects who take concomitant medications that are OAT1/OAT3 substrates and have a narrow therapeutic index may need to have their blood levels monitored for levels of the OAT1/OAT3 substrates after losmapimod dosing (see [Appendix 4](#)).

6. STUDY ASSESSMENTS AND PROCEDURES

Before performing any study procedures, all potential patients will sign an ICF. Patients will have the opportunity to have any questions answered before signing the ICF. The Investigator must address all questions raised by the patient. The Investigator or designee will also sign the ICF.

Patients continuing to Part B will sign and date an ICF before performing any study procedures for Part B of this protocol. Patient numbers will be maintained from Part A.

Study visits and the timing of assessments for the screening period or the treatment and follow-up periods are detailed in the schedules of assessments ([Table 7](#) and [Table 8](#)).

6.1. EFFICACY AND SAFETY ASSESSMENTS

Efficacy assessments will be performed during Part A and select efficacy assessments will also be performed during Part B [REDACTED] Select safety assessments ([Eliciting and Documenting Adverse Events](#), [Laboratory Analyses](#), [Vital Signs](#), [Physical Examinations](#), [Twelve-Lead Electrocardiograms](#)) will also be performed during Part B.

6.1.1. Reachable Workspace

The RWS Microsoft Kinect-based movement sensor system will be used at the visits noted in [Table 7](#) and [Table 8](#) to determine the patient's RWS.

The RWS is a 3D sensor-based system (using a single depth-ranging sensor) that can unobtrusively detect an individual's RWS and reflects individual global UE function, including shoulder and proximal arm. Previous and ongoing evaluation of the hardware and software system using a commercially available and cost-effective single sensor platform (Microsoft Kinect sensor) has demonstrated its high reliability, repeatability, face validity, feasibility, sensitivity to change, and promise as a COA for FSHD and other neuromuscular disorders ([Han et al. 2015](#)). Moderately impaired individuals with baseline RSA values between 0.20 and 0.70 (out of 1.0, for quadrants Q1-Q4) were more likely to show predictable declines over time with an annualized total RSA loss of 2.74% ($P=0.047$) ([Hatch, Chan, et al. 2019](#)). This study includes an inclusion criteria of screening total RSA (Q1-4) without weight between 0.20 and 0.70 to enrich for a population that is likely to change over a 1-year period.

During the evaluation, patients will be seated in front of the Microsoft Kinect sensor and will undergo a standardized upper extremity movement protocol under the supervision of a study clinical evaluator while looking at a video monitor. The evaluation will be performed with and without weights and on both the dominant and non-dominant arms. The Kinect sensor will track the 3D upper limb trajectory and transform the movements into a body-centric coordinate system. Each individual's RWS envelope will be reconstructed in a graphical output. Each body side's RWS envelope will be divided into 5 quintants, with the shoulder joint serving as the origin. The absolute total RWS surface envelope area (m^2) as well as areas for each of the

quadrants will be calculated. Scaling of the data by each person's arm length will allow normalization for comparison between patients (Han et al. 2015).

Instructions for equipment assembly, setup, testing, and site certification; a manual of operation; and a quick reference guide will be described in an RWS manual. A central reader will be responsible for training, quality control, data analysis, and standardization of the RWS across all sites in the study.

6.1.2. Skeletal Muscle Magnetic Resonance Imaging

Whole-body Dixon MRI for MFF, LMV, and MFI will be performed at the visits noted in [Table 7](#). Patients will be screened for any contraindications to MRI as per clinic standard practice. Patients can travel for MRI if needed, but the use of a study-approved MRI scanner should be consistent during the trial.

Details will be described in the study MRI manual. The study MRI manual will also describe in detail the steps involved in the acquisition, transmission, quality evaluation, and analysis of MRI images between the study site and the central reader.

6.1.3. Hand-Held Dynamometry

Dynamometry will be performed at the visits noted in [Table 7](#) and [Table 8](#). Quantitative isometric dynamometry (hand-held dynamometer) will be used to assess the skeletal muscle strength. Isometric dynamometry measures the static muscle strength without any movement.

Further details of the assessment will be provided in a study reference manual. All sites will use the same equipment and standardized testing procedure.

6.1.4. Eliciting and Documenting Adverse Events

AEs and SAEs will be assessed from the time the patient signs the ICF (for Part A and Part B) up to the last study visit, or up to 30 days after the patient has stopped study treatment, whichever is later, and SAEs must be reported to the Sponsor (or designee) by the Investigator without undue delay, but not later than 24 hours of obtaining knowledge of its occurrence (as described in [Section 7.3.2](#)). Any SAEs experienced after this period should be reported to the Sponsor (or designee) only if the Investigator suspects a causal relationship to the study drug.

At every study visit, patients will be asked a standard nonleading question to elicit any medically related changes in their well-being. They will also be asked if they have been hospitalized, had any accidents, used any new medications, or changed concomitant medication regimens (both prescription and over-the-counter medications).

In addition to patient observations, AEs identified from any study data (eg, clinically significant laboratory values, physical examination findings, ECG changes) or identified from review of other documents that are relevant to patient safety will be documented on the AE page in the eCRF.

AEs that occur during Part A will continue to be monitored until they are resolved or the patient is lost to follow-up. For those patients who rollover to Part B, ongoing AEs will continue to be monitored during Part B.

6.1.5. Laboratory Analyses

Samples for serum chemistry, hematology, and urinalysis will be collected at the time points specified in [Table 7](#) and [Table 8](#). Processing, storage, and shipping procedures for all clinical laboratory samples are provided in a laboratory manual. Sample collection details are presented in [Section 6.2.14](#). For the screening visit in Part A and the baseline visit in Part B, patients will be required to fast for at least 4 hours prior to laboratory blood samples being taken.

Any abnormal laboratory test results (hematology, clinical chemistry, or urinalysis) or other safety assessments (eg, ECGs, radiological scans, vital sign measurements), including those that worsen from baseline (ie, prior to first dose) and are felt to be clinically significant in the medical and scientific judgment of the Investigator, are to be recorded as AEs or SAEs. However, any clinically significant safety assessments that are associated with the underlying disease, unless judged by the Investigator to be more severe than expected for the patient's condition, are not to be reported as AEs or SAEs. Clinically significant abnormal laboratory test results will be reviewed by the Investigator and recorded as AEs or SAEs on the appropriate page in the eCRF.

If the laboratory reports are not transferred electronically, the values must be filed with the source information (including reference ranges). In most cases, clinically significant abnormal laboratory findings are those that are not associated with the underlying disease, unless judged by the Investigator to be more severe than expected for the patient's condition.

All laboratory tests with clinically significantly abnormal results during participation in the study or within 7 days after the last dose of investigational product should be repeated until the values return to normal or baseline or are no longer considered clinically significant by the Investigator.

All protocol-required laboratory assessments ([Table 6](#)) must be conducted in accordance with the laboratory manual and the Schedules of Assessments. If laboratory values from non-protocol-specified laboratory assessments performed at the institution's local laboratory require a change in patient management or are considered clinically significant by the Investigator (eg, SAE, AE, or dose modification), then the results must be recorded in the eCRF.

Blood and other biological samples will be collected for the clinical laboratory tests in [Table 6](#).

Table 6: Protocol-Required Laboratory Tests

Serum chemistry	Glucose, sodium, potassium, calcium, inorganic phosphate, total protein, albumin, blood urea nitrogen, creatinine, total bilirubin, direct bilirubin*, alkaline phosphatase, aspartate aminotransferase, alanine aminotransferase, gamma-glutamyltransferase, creatine phosphokinase
	*Direct bilirubin will only be tested in instances where total bilirubin is elevated. Direct bilirubin will be measured automatically by the central lab on the sample where total bilirubin is elevated. An additional sample is not required to be collected.

Hematology	Hemoglobin (including mean corpuscular volume), mean corpuscular hemoglobin, mean corpuscular hemoglobin concentration, hematocrit, red blood cell count, total white blood cell count, platelet count Differential blood counts, including basophils, eosinophils, neutrophils, lymphocytes, and monocytes
Urinalysis	Leukocytes, blood, nitrite, protein, urobilinogen, bilirubin, pH, specific gravity, ketones, glucose If there is a clinically significant positive result, urine will be sent for microscopy and/or culture.
Pregnancy	Serum beta human chorionic gonadotropin (all female patients of child-bearing potential), serum follicle-stimulating hormone (suspected postmenopausal female patients only [defined in Section 5.5.1]), urine pregnancy test (as required by local regulations)
Serology testing	Hepatitis B surface antigen, hepatitis C virus antibody, HIV-1/HIV-2 antibodies; tuberculosis will also be tested locally by QuantiFERON-TB Gold at Italian sites only (Appendix 2). Patients with a known history of hepatitis infection must be tested to confirm active infection. All patients will be tested for hepatitis B surface antigen and, if positive, will not be allowed to enroll in the study. All patients will also be tested for hepatitis C antibody and, if positive, should be tested for viral RNA. If the viral RNA test is negative, indicating inactive/resolved hepatitis C infection, then the patient can enroll in the study as long as their liver panel is within range of the inclusion and exclusion criteria (Section 4.1). If the viral RNA test is positive, indicating active viral hepatitis C, the patient will not be allowed to enroll in the study.
Urine drug screen	Cocaine, amphetamines, opiates (morphine), benzodiazepines, and cannabinoids Use of CBD/THC is permitted.

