7.2.2. Assessment of Causality

For each AE, the Investigator will determine whether there is a reasonable likelihood that the AE may have been caused by study drug according to the categories below. The Investigator's assessment of an AE's relationship to study drug is part of the documentation process, but it is not a factor in determining what is or is not reported in the study. If there is any doubt as to whether a clinical observation is an AE, the event should be reported.

The relationship or association of the study drug in causing or contributing to the AE will be characterized using the following classification and criteria:

Not related: This relationship suggests that there is no association between the study drug and the reported event.

Unlikely: This relationship suggests that the event is most likely produced by other factors such as the patient's clinical condition, intercurrent illness, or concomitant drugs administered to the patient, and does not follow a known response pattern to the study drug, or the temporal relationship of the event to study drug administration makes a causal relationship unlikely.

Possible: This relationship suggests that treatment with the study drug caused or contributed to the AE, ie, the event follows a reasonable temporal sequence from the time of drug administration or follows a known response pattern to the study drug but could also have been produced by other factors.

Probable: This relationship suggests that a reasonable temporal sequence of the event with drug administration exists, based upon the known pharmacological action of the drug, known or previously reported adverse reactions to the drug or class of drugs, or judgment based on the Investigator's clinical experience, the association of the event with the study drug seems likely. The event disappears or decreases on cessation or reduction of the dose of study drug.

Definite: This relationship suggests that a definite causal relationship exists between drug administration and the AE, and other conditions (concurrent illness, progression/expression of disease state, or concurrent medication reaction) do not appear to explain the event. The event reappears or worsens if the study drug is re-administered.

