7.7. CLINICAL LABORATORY CHANGES

Any abnormal laboratory test results (hematology, clinical chemistry, or urinalysis) or other safety assessments (e.g., ECGs, vital sign measurements), including those that worsen from baseline (i.e., prior to first dose) and are felt to be clinically significant in the medical and scientific judgment of the Investigator are to be recorded as AEs or SAEs. Clinically significant abnormal laboratory test results will be reviewed by the Investigator and recorded as AEs or SAEs on the appropriate page in the eCRF.

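### Protocol 6.1.5 exempts disease-associated laboratory findings of expected severity from AE reporting, while 7.7 and 6.1.4 require every clinically significant one to be recorded, so laboratory-related TEAE counts can depend on which section a site follows

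*Protocol*

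**What the plan says.** Protocol 6.1.5 (Laboratory Analyses) starts from a general rule: abnormal laboratory results and other safety assessments that the investigator considers clinically significant become AEs or SAEs. It then carves out "any clinically significant safety assessments that are associated with the underlying disease". Save where the investigator finds them worse than that patient's disease would explain, such findings "are not to be reported as AEs or SAEs". The sentence straight after the carve-out carries no such limit: "Clinically significant abnormal laboratory test results will be reviewed by the Investigator and recorded as AEs or SAEs on the appropriate page in the eCRF". The next paragraph adds a gloss, with the same severity limit attached: "In most cases, clinically significant abnormal laboratory findings are those that are not associated with the underlying disease".

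Protocol 7.7 (Clinical Laboratory Changes) covers the same ground in nearly the same terms. Abnormal results that "are felt to be clinically significant in the medical and scientific judgment of the Investigator are to be recorded as AEs or SAEs". It has no exception for the underlying disease. Protocol 6.1.4 also lists clinically significant laboratory values among the study data from which AEs are documented, again without an exception.

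Two further sections bear on the question. Protocol 7.1.1 keeps disease progression as such out of AE reporting unless a separate AE is involved. Protocol 7.3.1 requires progression to be reported only when it goes unexpectedly beyond the normal course. Yet 7.3.1 also says that a condition present at screening which deteriorates during the study should be recorded.

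SAP 10.3.1 builds the TEAE tables (by system organ class and preferred term, by maximum CTCAE grade and by relationship) from reported AEs.

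**The concern.** Both sections define when a laboratory abnormality becomes an AE. They give opposite instructions for one class of result, neither refers to the other, and no precedence is stated. Two sites holding the same protocol can handle the same result differently and each point to a section that supports it.

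What is at stake is the case definition behind the laboratory terms in the TEAE tables, collected at about 36 sites. An event that was never entered cannot be recovered at analysis. For example, the SAP 9.3.4.1 convention that missing relatedness is treated as related works only on events that are in the database. The same recording rule feeds Part B, where AEs and laboratory tests are part of the primary safety endpoint.

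**Working it through.** The documents state no figure for this point, so the check is a comparison of texts followed by a trace into the SAP outputs.

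**Step 1. Apply each rule to the three kinds of clinically significant laboratory result.**

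| Source | Not disease-associated | Disease-associated, worse than expected | Disease-associated, expected severity |
|---|---|---|---|
| Protocol 6.1.4 | record | record | record |
| Protocol 6.1.5, carve-out | record | record | **do not report** |
| Protocol 6.1.5, sentence after the carve-out | record | record | record |
| Protocol 7.7 | record | record | record |
| Protocol 7.1.1 (progression as such) | not addressed | not an AE by itself | not an AE by itself |
| Protocol 7.3.1 (progression) | not addressed | report if unexpected | not required |
| Protocol 7.3.1 (present at screening) | record if it deteriorates | record if it deteriorates | record if it deteriorates |

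For the laboratory rules in 6.1.4, 6.1.5 and 7.7, the first two columns agree. The contradiction lies in the last column: the 6.1.5 carve-out against 7.7, 6.1.4 and the following sentence of 6.1.5 itself. The more general sections 7.1.1 and 7.3.1 do not settle it. Their progression sentences lean towards an exception, while the deterioration sentence in 7.3.1 leans towards recording.

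**Step 2. Trace the affected results into the planned outputs.**

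- Affected: the TEAE tables of SAP 10.3.1 and, in principle, the SAE tables of 10.3.2, because both rest on what sites enter.
- Not affected: potential drug-induced liver injury, which SAP 9.3.4.1 derives from laboratory values and expressly not from the AE records; the counts of ALT and AST at or above 3 times ULN and bilirubin at or above 2 times ULN (SAP 10.3.4); and the ALT and AST shift tables (SAP 10.3.5).
- CPK: it is in the chemistry panel (Protocol Table 6), and Protocol 5.8 asks for particular attention to it when a statin is started. It is missing from the shift-table list in SAP 10.3.5. It keeps by-visit summaries of values and changes, and listings. Outside the AE tables, no categorical summary of CPK by arm is specified.

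**Step 3. Direction of the effect.** Let p1 and p0 be the true event proportions on losmapimod and placebo, and f the fraction of events that sites record. If f is the same in both arms, the recorded difference is

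f × p1 − f × p0 = f × (p1 − p0),

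which shrinks towards zero as f falls, while the ratio p1/p0 is unchanged. A common f is plausible in Part A because investigators are blinded, but it is an assumption.

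**Step 4. Size.** Neither f nor the rate of disease-associated, clinically significant results appears in the documents. The Phase 2 counts in Protocol 1.3.2.1 (AEs of increased ALT in 5/14 in the open-label study, and 2/40 versus 0/40 in ReDUX4) defined the event as any value above ULN. That is not the investigator-judged clinical significance used here, so those counts cannot supply the missing rate.

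**The case against.** The strongest reply is that the gap is narrow and the exception reasonable. The carve-out does not apply when a finding is worse than expected. The gloss in 6.1.5 suggests that most clinically significant findings are not disease-associated to begin with. Sections 7.1.1 and 7.3.1 also keep ordinary progression out of AE reporting. All of this stands, and it means that 6.1.5 is not simply an outlier. It narrows the conflict without removing it: 7.7 sits in the AE chapter, where a site would look, and nothing there points back to an exception.

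The second reply is that liver safety is already protected by laboratory-derived outputs. That stands in full for potential DILI, the threshold counts and the ALT/AST shift tables.

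A reader might infer more than the documents support in two respects.

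- **That FSHD itself raises ALT, AST or CPK, so that a liver signal would be written off to disease.** No section says that FSHD raises these enzymes. The only controlled FSHD data cited show no increased ALT in the 40 ReDUX4 placebo patients. The conflict applies to any result that a site attributes to the disease, and naming particular analytes as the ones affected would be an assumption.
- **That the carve-out breaches Protocol 7.2.2**, which says of the causality assessment that "it is not a factor in determining what is or is not reported in the study". That sentence concerns relationship to study drug. The carve-out asks about association with the disease and about severity. The two judgements overlap in practice, but there is no formal breach.

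**Conclusion.** The inconsistency is real and confined to one class: clinically significant laboratory results (and other safety findings covered by both sections) that a site associates with FSHD and judges to be of expected severity. For these the protocol cannot be followed as written, and the laboratory-related TEAE counts can depend on the section a site uses.

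The consequence is inconsistent or diluted counts. They are probably similar in the two arms, on the assumption that blinded investigators attribute results to disease at the same rate in each. CPK is the most exposed analyte for the reason given in Step 2.

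A reader might be tempted to express the loss as reduced power to show an imbalance between arms. The documents do not support such a figure: the event rates and the fraction left unrecorded would both have to be invented, and the planned AE analysis is descriptive, with no between-arm test. This is a correction to the recording rule and does not show that a safety signal would be missed.

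**What to change.** Reconcile Protocol 6.1.4, 6.1.5 and 7.7 into one recording rule. State it once in 6.1.5, remove the contradiction between the carve-out and the sentence after it, and have 7.7 cross-refer to 6.1.5 instead of restating the rule. The rule should say expressly whether the disease-association exception applies to a laboratory value that worsens from the pre-dose baseline, so that it also fits the deterioration sentence in 7.3.1. Tell sites by clarification letter.

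Optionally, add CPK to the biochemistry parameters in the SAP 10.3.5 shift tables, so that a categorical CPK summary exists that does not rely on AE reporting.

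The cost is protocol wording, one letter and, if taken up, one more shift table. The downside is possibly some extra non-serious AE records. The letter would not by itself harmonise records entered before it.
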